4.2 Selection of Study Population

4.2.1 Inclusion Criteria

	Inclusion Criteria	Rationale	Screening	Enrollment V2
1.	Subject has signed the ICF.	Administrative	Х	
2.	Smoking, healthy subject based on safety laboratory, ECG, spirometry, vital signs, physical examination, medical history and Investigator's assessment.	Safety	X	
3.	Subject has been smoking for at least three years prior to V1.	Effect	Х	
4.	Subject has been smoking \geq 10 cigarettes per day over the last 12 months. Smoking status will be verified by a urinary cotinine \geq 200 ng/mL and CO exhaled breath test > 6ppm both at V1 and V2.	Effect	X	X
5.	Subject does not plan to quit smoking within 6 months after V1.	Safety	х	

Subjects who meet all the following inclusion criteria can be enrolled into the study:

Confidentiality Statement

Philip Morris Products SA.	Statistical Analysis Plan	Confidential
P1-EXC-01-EU	Final 2.0	Page 17 of 71
Dalata data DMI DDD WIZI 112407		

Related to PMI-RRP-WKI-112487

SAP_P1-EXC-01-EU

	Inclusion Criteria	Rationale	Screening	Enrollment V2
6.	Subject is aged between 21 and 65 years (inclusive).	Safety	Х	
7.	Subject is available for the entire study period and willing to comply with study procedures.	Effect	Х	

Confidentiality Statement

PMI RESEARCH & DEVELOPMENT

4.2.2 Exclusion Criteria

Subjects who meet any of the following exclusion criteria must not be enrolled into the study:

	Exclusion Criteria	Rationale	Screening	Enrollment V2
1.	Subject has a clinically relevant disease which requires medication (including but not limited to gastrointestinal, renal, hepatic, neurological, hematological, endocrine, oncological, urological, immunological, pulmonary [such as but not limited to pulmonary oedema, asthma], and cardiovascular [such as, but not limited to myocardial infarction, unstable angina, uncontrolled arrhythmias, heart failure], disease) or any other clinically significant medical condition (including abnormal safety laboratory result as per CTCAE), which as per the judgment of the Investigator would jeopardize the safety of the subject.	Safety	X	
2.	Subject who has forced expiratory volume in 1 second/forced vital capacity (FEV ₁ /FVC) <0.7 and FEV ₁ <80% predicted value at post- bronchodilator spirometry (GOLD, 2017).	Safety	X	
3.	Subject with asthma condition (FEV ₁ /FVC < 0.75 and reversibility in FEV ₁ (in both > 12% and > 200 mL) from pre to post-bronchodilator values.	Safety	X	
4.	Subject has clinical significant abnormalities of ECG at V1.	Safety	х	
5.	Subject performs more than 45 min of vigorous physical activity per week.	Effect	х	
6.	Inability to perform a VO ₂ max test at V1.	Safety	Х	
7.	$VO_2max >50$ mL.min ⁻¹ kg ⁻¹ for men and $VO_2max >40$ mL.min ⁻¹ kg ⁻¹ for women as determined at V1.	Effect	х	
8.	Subject takes medication influencing blood volume such as erythropoietin, diuretics and beta blockers, or diabetic medications.	Effect	х	

Confidentiality Statement

Philip Morris Products SA.

P1-EXC-01-EU

Statistical Analysis Plan Final 2.0 Confidential

Page 19 of 71

Related to PMI-RRP-WKI-112487

SAP_P1-EXC-01-EU

	Exclusion Criteria	Rationale	Screening	Enrollment V2
9.	Subject cannot participate in the study for any reason other than medical as per the Investigator's judgment (e.g. psychological and/or social reason)	Administrative	Х	
10.	For women only: subject is pregnant (does not have negative pregnancy tests at V1 and at V2) or is breastfeeding.	Safety	Х	Х
11.	For women of childbearing potential ¹ : female subject who does not agree to using an acceptable method of effective contraception ² during the entire study.	Safety	Х	
12.	Subject has a BMI < 18.5 kg/m ² or BMI \ge 30 kg/m ² .	Safety	Х	
13.	Subject has positive serology test for HIV, Hepatitis B or Hepatitis C.	Safety	Х	
14.	Subject has a positive alcohol breath test and/or a history of alcohol use disorder (both V1 and V2).	Administrative	Х	х
15.	Subject has a positive urine drug screen.	Administrative	х	х
16.	The subject has been previously screened for this study.	Administrative	Х	
17.	The subject, or one of their family members (e.g., spouse, parent, sibling or child), is a current or former employee of the tobacco industry.	Administrative	Х	
18.	The subject, or one of their family members (e.g. spouse, parent, sibling or child), is an employee of the investigational site or any other parties involved in the study.	Administrative	Х	
19.	Subject is legally incompetent, or physically or mentally incapable of giving consent (e.g., emergency situation, under guardianship, prisoners, or subjects who are involuntarily incarcerated).	Administrative	Х	

¹ Women who are not of childbearing potential meet at least one of the following criteria: Have undergone hysterectomy or bilateral tubal ligation, Have medically confirmed ovarian failure, or Are medically confirmed to be post-menopausal (cessation of regular menses for at least 12 consecutive months with no alternative pathological or physiological cause).

Confidentiality Statement

² Intrauterine device, intrauterine system, barrier methods of contraception (condoms, occlusive caps) with spermicidal foam/gel/film/suppository, hormonal contraception containing progesterone only, vasectomized partner(s), from screening until the end of the safety follow-up period.

Philip Morris Products SA.	Statistical Analysis Plan	Confidential
P1-EXC-01-EU	Final 2.0	Page 20 of 71
Related to PMI-RRP-WKI-112487		CAD DI EVO 01 EU

4.3 Product Allocation and Blinding

4.3.1 Method of Assigning Subjects to Sequence/Product Arms

Randomization will be done through the at any time during the baseline visit. Subjects will be informed about their study arm allocation at the end of V3. Subjects will be randomized in one of the four study arms:

- Cigarette arm with training program
- IQOS-1 arm with training program
- SA arm with training program •
- IQOS-2 arm without training

in a 5:5:5:3 ratio using a stratified randomization based on daily cigarette consumption over the 12 months prior to V1 (10-19 cigarettes/day vs. >19 cigarettes/day), and sex. All subjects will be instructed to adhere to their assigned product/regimen until they complete the study.

4.3.2 Blinding

4.3.2.1 Blinding of site staff

This is an open-label study and the site staff performing study assessments will therefore not be blinded to the randomized arm of the subject.

4.3.2.2 Blinding of data

There will be additional, even though limited, degree of blinding during the conduct of the study, including the data review and data analysis process prior to database lock. In particular, PMI and contract research organization (CRO) personnel will be blinded as summarized in Table 1.

Confidentiality Statement

Philip Morris Products SA.	Statistical Analysis Plan	Confidential
P1-EXC-01-EU	Final 2.0	Page 21 of 71
Related to PMI-RRP-WKI-112487		SAP_P1-EXC-01-EU

Table 1: Blinding

Blinded Study Personnel	Blinded data	End of Blinding Period
PMI and CRO Study Statisticians	VO ₂ max and exercise capacity test results after randomization	After database lock.
PMI Clinical Scientist	VO ₂ max and exercise capacity test results after randomization	After the finalization of PMI blind database review. Can be actively un-blinded when appropriate.

Any PMI and CRO personnel who are not listed in Table 1 will by default be not be blinded. Unblinded information will not be shared with the blinded study team, until the end of the blinding period. PMI will receive blinded and unblinded data for the pre-analysis data review as planned in the data review plan. Unblinded data will only be reviewed by the unblinded study team.

4.3.3 Compliance to Product Allocation

Subjects will enter the number of HeatSticks, cigarettes, or/and other tobacco and nicotine containing products used per day in a product use diary from V2 until the discharge at V43.

5 DERIVED AND COMPUTED VARIABLES

5.1 Urinary Biomarkers

Spot urine will be collected to measure concentrations of NEQ, NNAL, CEMA and creatinine.

5.1.1 Nicotine Equivalents

The concentration of NEQ in spot urine will be derived according to the formula below, and considering the conversion factors described in Table 2: Conversion factors from ng/ml into μ mol/L. The concentrations reported for free nicotine and its five major metabolites will not be used individually as analysis variables.

Neq [mg/L] = (free nicotine[µmol/L] + nicotine-glucuronide [µmol/L] + free cotinine [µmol/L] + cotinine-glucuronide [µmol/L] + free *trans*-3'-hydroxycotinine [µmol/L] + *trans*-3'-hydroxycotinine-glucuronide [µmol/L])

Confidentiality Statement

Philip Morris Products SA.	Statistical Analysis Plan	Confidential
P1-EXC-01-EU	Final 2.0	Page 22 of 71
Related to PMI-RRP-WKI-112487		

*162.2[µg/µmol] / 1000

	•					
l able 2:	Conversion	factors	trom	ng/ml	Into	µmol/L

	Molecular weight (g/mol)	Conversion factor from ng/mL to µmol/L
Free Nicotine	162.232	0.006164
Nicotine glucuronide	338.356	0.002955
Free Cotinine	176.218	0.005675
Cotinine-glucuronide	352.341	0.002838
Free Trans-3'hydroxycotinine	192.217	0.005202
Trans -3'hydroxycotinine-glucuronide	368.34	0.002715

5.1.2 Biomarkers of Exposure adjusted for Creatinine

The adjustment for creatinine for the urinary BoExp will be calculated as:

 $\left[BoExp (creatinine adjusted) = \frac{BoExp}{Creatinine}\right]$

NEQ, Total NNAL, CEMA will be expressed in mg/g creat, pg/mg creat and ng/mg creat respectively.

5.2 Blood composition as determined by CO re-breathing method

Blood composition variables as determined by CO re-breathing method will be calculated according to the method proposed in Siebenmann (Siebenmann, et al. 2017). The corresponding endpoints are hemoglobin mass (g), red blood cell volume (mL), plasma volume (mL) and total blood volume (mL).

The change in the fraction of carboxyhemoglobin in blood samples obtained pre- and post-CO rebreathing is calculated in percentages as:

 $\Delta COHb = \% COHbPost - \% COHbPre.$

Confidentiality Statement

Philip Morris Products SA.	Statistical Analysis Plan	Confidential
P1-EXC-01-EU	Final 2.0	Page 23 of 71
Related to PMI-RRP-WKI-112487		

The absorbed number of CO molecules is calculated in moles as: nCOabsorbed = Patm * VCOabsorbed/(R * T)where R is the ideal gas constant [0.008206 L*atm/(mol*K)]. The volume of CO that has been absorbed (VCOabsorbed), atmospheric pressure (Patm), and room temperature (T) should be entered in liters, atmospheres, and Kelvin, respectively.

The value of the volume of CO that is absorbed is normalized to 25 C° and 1013 mbar (i.e. 1 atm) and called VCOabsorbed, norm. Thus in the equation above Patm = 1 atm and T = 298.15K. The absorbed number of CO molecules is therefore,

nCOabsorbed = 1* VCOabsorbed,norm / (82.06 *298.15) = VCOabsorbed,norm / 24466.189.

Given that 1 mol of hemoglobin binds 4 mol of CO the tagged number of hemoglobin molecules (nHbtagged) is calculated in moles as:

nHbtagged = nCOabsorbed/4.

The total number of hemoglobin molecules is calculated in moles as: nHbtotal = (nHbtagged/ Δ COHb) * 100.

Based on the molar mass of hemoglobin, the hemoglobin mass (in grams) is calculated as: Hbmass = nHbtotal * 6.44×10^4 g/mol. With the equations above, a VCOabsorbed, norm of 90 mL and a $\triangle COHb$ of 10 % results in 592.25 g HBmass.

Intravascular volumes (in mL) are calculated as: Red blood cell volume, i.e. RBCV = Hbmass * Hct/[Hb] Total blood volume, i.e BV = RBCV/Hct Plasma volume, i.e PV = BV - RBCVHct is entered in these equations as absolute fractions (i.e., not in %), whereas [Hb] is entered in g/mL.

5.3 Questionnaires

5.3.1 Fagerström Test for Nicotine Dependence (Revised Version)

Subjects will complete the FTND questionnaire in its revised version (Heatherton, et al. 1991).

Confidentiality Statement

Philip Morris Products SA.	Statistical Analysis Plan	Confidential
P1-EXC-01-EU	Final 2.0	Page 24 of 71
Related to PMI-RRP-WKI-112487		SAP_P1-EXC-01-EU

The questionnaire consists of six questions. The FTND total score determines the subject's dependence on nicotine in three levels: mild (0-3 points), moderate (4-6 points), and severe (7-10 points).

The responses are scored as defined in the Table 3 below and the sum score (FTND score) will be calculated.

Item No.	Question	Response	Score
1	How soon after you wake up do you smoke	within 5 min	3
	your first cigarette?	6-30 min	2
		31-60 min	1
		after 60 min	0
2	Do you find it difficult to refrain from smoking	Yes	1
	in places where it is forbidden?	No	0
3	Which cigarette would you hate most to give up?	The first one in the morning	1
		Any other	0
4	How many cigarettes do you smoke per day?	1 to 10	0
		11 to 20	1
		21 to 30	2
		31 to 40	3
		More than 40	3
5	Do you smoke more frequently during the first	Yes	1
	hours after waking than during the rest of the day?	No	0
6	Do you smoke if you are so ill that you are in	Yes	1
	bed most of the day?	No	0

Table 3: Scoring of Responses to the Fagerstöm Test for Nicotine Dependence

5.3.2 Product Preference

On V3, the following question will be asked to all subjects:

"Which product would you prefer to be randomized to?"

- IQOS
- Cigarette
- Smoking abstinence
- No preference

Confidentiality Statement

Philip Morris Products SA.	Statistical Analysis Plan	Confidential
P1-EXC-01-EU	Final 2.0	Page 25 of 71
Related to PMI-RRP-WKI-112487		SAP_P1-EXC-01-EU

5.3.3 Lifestyle questionnaire

Subjects will be asked questions to capture baseline covariates such as, diet, alcohol intake, sleep deficit, and exposure to passive smoking at V3.

5.3.4 Assessment of Cough-VAS and Likert Scales

Subjects will assess cough on a Visual Analogue Scale (VAS) and on three Likert scales.

Subjects will be asked if they have experienced a regular need to cough (*e.g.*, whether they have coughed several times in the previous 24 hours prior to assessment). If the answer is 'yes', subjects will be asked to complete a VAS and 3 Likert scales. On the VAS, subjects will assess how bothersome their cough was during the previous 24 hours. The VAS ranges from "not bothering me at all" to "extremely bothersome". Furthermore, subjects will assess the intensity and frequency of cough and the amount of sputum production during the previous 24 hours on Likert scales.

- The intensity of cough will be assessed on a 5-point Likert scale ranging from 1 to 5, with 1 = very mild 2 = mild 3 = moderate 4 = severe 5 = very severe.
- The frequency of cough will be assessed on a 5-point Likert scale ranging from 1 to 5, with 1 = rarely 2 = sometimes 3 = fairly often 4 = often 5 = almost always.
- The amount of sputum production will be assessed on a 4-point Likert scale ranging from 0 to 3, with 0 = no sputum 1 = a moderate amount of sputum 2 = a larger amount of sputum 3 = a very large amount of sputum.

5.3.5 International Physical Activity Questionnaire (IPAQ) - short form

At V1 subjects' physical activity levels will be assessed using the short version of the IPAQ. The short form records the activity of four intensity levels:

- vigorous-intensity activity such as aerobics,
- moderate-intensity activity such as leisure cycling,
- walking, and
- sitting.

The categorical score of the short question of the IPAQ will be presented using the following algorithm, further details can be found in (IPAQ 2005).

1. Low

No activity is reported OR Some activity is reported but not enough to meet Categories 2 or 3.

Confidentiality Statement

Philip Morris Products SA.	Statistical Analysis Plan	Confidential
P1-EXC-01-EU	Final 2.0	Page 26 of 71
Related to PMI-RRP-WKI-112487		SAP P1-EXC-01-EU

2. Moderate

Either of the following 3 criteria

• 3 or more days of vigorous activity of at least 20 minutes per day OR

• 5 or more days of moderate-intensity activity and/or walking of at least 30 minutes per day OR

• 5 or more days of any combination of walking, moderate-intensity or vigorous intensity activities achieving a minimum of at least 600 MET-minutes/week.

3. High

Any one of the following 2 criteria

• Vigorous-intensity activity on at least 3 days and accumulating at least 1500 MET-minutes/week OR

• 7 or more days of any combination of walking, moderate- or vigorous-intensity activities accumulating at least 3000 MET-minutes/week

5.3.6 Borg Rate of Perceived Exertion (RPE) Scale

During VO_2max test (only at V3 and V43) subjects will rate their perceived exertion on the Borg RPE scale at rest and then at each 25W increase (Borg 1982). The Borg RPE scale is a way of measuring physical activity intensity level. It is based on the physical sensations a person experiences during physical activity, including increased heart rate, increased respiration or breathing rate, increased sweating, and muscle fatigue.

The scale ranges from

- 6- no exertion at all,
- 7.5 extremely light,
- 9 very light,
- 11 light,
- 13 somewhat hard,
- 15- hard,
- 17-very hard,
- 19- extremely hard, to
- 20- maximal exertion.

A high correlation exists between a person's perceived exertion rating times 10 and the actual heart rate during physical activity.

5.3.7 Rate of Perceived Capacity (RPC) Scale

To predict maximal exercise capacity, the rating of perceived capacity (RPC) scale was developed based on metabolic equivalents (METs) (Wisen, Farazdaghi and Wohlfart 2002).

Confidentiality Statement

Data and information contained in this document are considered to constitute trade secrets and confidential commercial information, and the legal protections provided to such trade secrets and confidential information are hereby claimed under the provisions of applicable law. No part of this document may be publicly disclosed without the written consent of Philip Morris Products S.A

Total number of pages of the document doesn't include the signature page

Philip Morris Products SA.	Statistical Analysis Plan	Confidential
P1-EXC-01-EU	Final 2.0	Page 27 of 71
Related to PMI-RRP-WKI-112487		

MET values from 1 to 20 for men and 1 to 18 for women are listed on a progressive scale and linked to physical activities. Subjects will rate their perceived capacity by choosing the most strenuous activity and the corresponding MET value that they could sustain for 30 min.

5.3.8 Product Use Diary

Subjects will enter the number of HeatSticks, cigarettes, or/and other tobacco and nicotinecontaining products used per day in a product use diary from V2 until discharge at V43.

5.3.9 Qualitative Interviews on Health and Functioning (sub-study)

Subjects that have signed the optional section of the ICF for the sub-study on health on functioning will have a one-hour, qualitative interview over the phone or computer between V2 and V3, and at the end of the study between V42 and V43. Questions during the interview will be open-ended and will focus on subjects' current state of health and functioning, experiences during the training program, and changes in health and functioning as a result of the training program.

5.4 Categorical Variables

For categorical variables used in this study see Section 9.1.1 "Stratified Presentation".

5.5 Product Use

The number of Cigarettes, Heatsticks, and other nicotine/tobacco containing product used daily, as reported by the subject and collected in the electronic diary or paper CRF, will be used to monitor product use and evaluate adherence to product allocation.

Additionally, BoExp measured in the study will be used to fine tune product use allocation as an exploratory analysis.

5.5.1 Product Use Pattern

Actual product use pattern categorization is described in Figure 2 below,

Confidentiality Statement

Figure 2: Product Use Categorization

Note: HS: HeatSticks

The calculation of product use categories will be performed based on Figure 2. For each subject we will calculate product use for two time periods, representing Week 1 use and average product consumption from V3 till end of Month 3 or last visit prior to early termination whichever comes first.

- From V3 to V4: Week 1
- From V3 to V43/Last visit before early termination: Overall average consumption

For each time period the daily product use reported by a subject in the study will be summed up and averaged by the actual number of days the subject was in the study after randomization until date of last reported product use within the respective time period. This will then be multiplied by 30 to describe the average monthly product use.

For subjects who early terminated from the study, product use for overall average consumption will be calculated until the last visit prior to V44. For example, if a subject early terminated at V23 and subsequently came for V44, then product use will be calculated from V3 until the date of V23.

As both electronic diaries and paper diaries were used in the study concurrently for some subjects, the following rules will be applied in case of inconsistencies.

Confidentiality Statement

Philip Morris Products SA.	Statistical Analysis Plan	Confidential
P1-EXC-01-EU	Final 2.0	Page 29 of 71
Related to PMI-RRP-WKI-112487		SAP_P1-EXC-01-EU

- When there is data available for both electronic and paper diaries for the same date, the electronic diary data will be kept if both are the same. If the data is different on the same date, then data for this date will be considered missing.
- If a subject reports no product use but a value is recorded, we will assume that the number of product used reported was correct and use it in the derivation of product use.

Missing data for self-reported daily use will not be imputed and we will assume that the derived average monthly use from non-missing data is representative of the actual usage. For each analysis period (Week 1 or Overall), if more than 50% of product use data is not available then the subject will be grouped into the 'Others' product use arm. Therefore, it is possible that a subject is not considered for statistical modelling as it is grouped into 'Others' for Week 1 (3 out of 7 days of product use data only) but available for analysis for the entire study period if more than 50% of product use data was eventually collected throughout the study. A subject may have switched product use groups throughout the study and the total number of subjects in an arm may fluctuate over time depending on the actual product use.

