## 6.3.1 From Enrollment to Randomization

From screening visit (V1) to randomization (V3), all subjects will be allowed to continue smoking *ad libitum* their preferred usual brand of cigarettes. 30-60 min before start of baseline VO2 max at V3, subjects will smoke a cigarette. However, subjects will never be forced to smoke, and will only smoke if they are willing to.

At randomization, subjects allocated to the *IQOS* arm, since they will not be able to purchse the device on time to start the trial (there is no physical store in the study area), will be supplied with an *IQOS* starter kit (*i.e.*, *IQOS* device and a selection of HeatStick variants available on the German market). Subjects will benefit from a guided trial to understand how to properly use the device and will have to return it at the end of the trial. Subjects will have to purchase their own HeatSticks for use during the study (available throughout the country).

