A demonstration of *IQOS* and the mHealth wearable will be done by the site staff during the screening visit. All inclusion and exclusion criteria will be assessed. A VO₂max test will be performed as part of eligibility assessments. All eligible subjects will be invited to come to V2.

Enrollment and Familiarization, V2 (7 ± 1 days prior to V3): Enrollment will take place after confirmation of smoking status (urine cotinine and exhaled CO) and negative urine pregnancy test, alcohol breath test and urine drug screen. After enrollment, vital signs will be assessed and subjects will perform an exercise capacity test for the purpose of familiarization. The exercise test consists of completing a pre-defined work (calories) on a bike ergometer (1). Before leaving the investigational site the subject will receive a mHealth wearable kit and will be trained on how to handle the device. Subjects will be instructed to wear the device all the time. Subjects will also receive a diary to record the daily use of tobacco and nicotine containing products.

Between V2 and V3, subjects having signed the optional section of the ICF will have an interview (by phone or computer) on the topic of health and functioning lasting around 60 minutes.

Baseline and Randomization, V3: Baseline assessments will be performed as listed in Appendix 1. Then, 30-60 min before start of the VO2max test all subjects will smoke a cigarette (only if they are willing to). During the VO2max test at rest and at each 25 W increase, the subject's lactate levels will be determined by capillary blood sampling and the rate of perceived exertion (RPE) will be assessed using the Borg RPE scale. After completing the VO2max test, the subject will rest for 60±5min, after which the exercise capacity test will be performed. After completing exercise tests, total blood volume will be determined.

Subjects will thereafter be randomized into one of the 4 arms. Subjects randomized into *IQOS* arms will receive their *IQOS* starter kit and be trained on how to use the device. Subjects randomized into the SA arm will receive smoking abstinence support and will be allowed to use NRT upon request.

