8.4 As Exposed Biochemically and Exercise Compliant Set

A subset of the AEECS based on biochemical verification of smoking status (AEBECS) will be analysed based on actual arm as determined with these additional criteria.

For a subject to be classified as smoking abstinent, in addition to the product use diary with an average cigarette use at max 5 Cigarettes/month the following will be used,

- No CO breath test > 6 ppm at three consecutive visits from V3 onwards.
- Total NNAL concentration < 75.9 pg/mL in spot urine (Berg, et al. 2012) at two or more visits collected from V3 onwards.
- CEMA concentration adjusted for creatinine < 40 ng/mg creat (Claussen, et al. 2019) in spot urine at two or more visits collected from V3 onwards.

The following biochemical verification will be used in addition to the product use diary to further fine tune subjects in the IQOS user group.

- No CO breath test > 6 ppm at three consecutive visits from V3 onwards.
- Total NNAL concentration < 75.9 pg/mL in spot urine at two or more visits collected from V3 onwards.
- CEMA concentration adjust for creatinine < 40 ng/mg creat in spot urine at two or more visits collected from V3 onwards.

8.5 **Protocol Deviations**

All protocol deviations will be listed and also summarized based on the classification of deviation type for subjects in the Safety Set.

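### SAP 5.5.1 does not exclude the V3 date from the product-use windows, so cigarettes smoked before randomisation can move a fully abstinent SA subject out of the SA group at V4

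*SAP*

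**What the plan says.** SAP 5.5.1 defines two windows for classifying actual product use: "From V3 to V4: Week 1" and "From V3 to V43/Last visit before early termination: Overall average consumption". Within each window, "the daily product use reported by a subject in the study will be summed up" and then "averaged by the actual number of days the subject was in the study after randomization", up to the last reported use in the window. The result is multiplied by 30 to give a monthly figure. The reference to randomisation qualifies the number of days, not the use being summed. The early-termination example in the same section also starts its window at V3. SAP 5.5.2 and 5.5.3 use V3 both to end the V2-V3 average and to start the later averages, without saying which one owns that date.

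On the V3 day itself, Protocol 6.3.1 says that "all subjects will be allowed to continue smoking" as they wish up to randomisation. SAP 4.1 adds one cigarette 30 to 60 minutes before the VO2max test, for those willing. Protocol 9.3 places all baseline assessments before randomisation, and Protocol 6.4 and SAP 4.3.1 have subjects told their arm at the end of V3. Product counts are recorded as the number "used per day in a product use diary from V2 until the discharge at V43" (SAP 4.3.3), with no time of day.

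The only abstinence limit visible in the text is in SAP 8.4: "average cigarette use at max 5 Cigarettes/month".

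**The concern.** The numerator can contain smoking from before randomisation, while the denominator counts only days after it. This happens with a complete diary, so it is separate from the rules on missing entries.

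The variable matters because the AEECS, the main non-safety set, is analysed by actual arm (SAP 8.3, 9.1.1, 9.6.1). SAP 5.5.1 itself describes a subject who drops out of the modelling because of the Week 1 category alone, and SAP 9.6.1.2 ties the acute baseline to the Week 1 group. The V4 tables for VO2max and exercise capacity in the AEECS are flagged as topline (SAP 13.2). An SA subject who complied fully from randomisation could therefore be lost from the SA group at V4 because of baseline smoking. Those who remain would be selected partly on how little they smoked that morning. The arm is small, with 25 randomised and 20 planned as evaluable, so each subject lost is 1/20 = 5% of the planned number.

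**Working it through.** **The plan's own figure.** SAP 5.5.1 gives 3 of 7 diary days as an example of more than 50% missing. The missing share is 4/7 = 57.1%, so the example reproduces on a 7-day Week 1. It does not settle the boundary. At nominal timing, V3 through the day before V4 is 7 dates, and the day after V3 through V4 is also 7 dates. Counting both ends gives 8.

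**Inputs.**
- k = cigarettes reported on the V3 date. Not given in the documents; 1 to 10 is assumed here, because entry requires at least 10/day (Protocol 5.1.1).
- D = days in the Week 1 window: 5 to 9, from V4 at 7±2 days after V3 (SAP 4.1). The diary is taken as complete to V4.
- Limit = 5 cigarettes/month (SAP 8.4), assumed to apply also to the AEECS categories.
- Smoking after randomisation = 0.

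**Formula.** Monthly use = 30 × k / D. It exceeds 5 when k > D/6.

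| k | D=5 | D=6 | D=7 | D=8 | D=9 |
|---|---|---|---|---|---|
| 1 | 6.0 | 5.0 | 4.3 | 3.75 | 3.3 |
| 2 | 12.0 | 10.0 | 8.6 | 7.5 | 6.7 |
| 5 | 30.0 | 25.0 | 21.4 | 18.75 | 16.7 |
| 10 | 60.0 | 50.0 | 42.9 | 37.5 | 33.3 |

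Two or more cigarettes on V3 exceed the limit at every permitted V4 date. If V3 is also counted as a day, the longest window becomes 10 days and two cigarettes still give 30 × 2/10 = 6.0. One cigarette exceeds the limit only at D=5; at D=6 it equals the limit, which is allowed.

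**Overall window.** With 106 days, 10 cigarettes on V3 give 30 × 10/106 = 2.83, 17 give 4.81 and 18 give 5.09. A fully abstinent subject therefore needs at least 18 V3 cigarettes to fail.

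**With V3 excluded.** The same subject has 0/month in both windows, whatever was smoked on V3.

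**The case against.** The strongest reply is that the SAP never states that the V3 date is counted, and that several places lean towards a post-randomisation reading. The denominator is days after randomisation. Week 1 is treated as 7 days. SAP 9.1.3.1 calls Week 1 the period between V3 and V4 and starts Months 2 and 3 on the day after the boundary visit. The cigarette covariate in SAP 9.6.1.1.1 runs from randomisation. It is fair to call this an unresolved boundary and not a declared rule. But none of these places removes the V3 entry from the sum, and two programmers could derive different V4 arms from the same text. The SAP does set such rules elsewhere: besides 9.1.3.1, SAP 9.1.6 drops the first and last wearable days as possibly incomplete. The diary has no equivalent.

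Second, a reader might infer that the cigarette requested before the test is enough to misclassify SA subjects. It is not. It is optional, and alone it gives 4.3/month at the nominal 7 days. The problem generally needs a second cigarette, whose frequency is unknown, though it is plausible in people smoking at least 10/day.

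Third, the limit of 5/month is stated for the biochemically verified subset, which is exploratory. SAP 8.4 presents it as the diary criterion to which biochemical tests are added, so applying it to the AEECS is reasonable, but Figure 2 cannot be checked. A reader might also infer that IQOS subjects drift into dual use, or that the V4 contrasts shrink by a known amount. The dual-use cut-offs and the category a failing SA subject would enter are not visible, so neither can be shown. If that category were the Others group, SAP 9.4 would leave the subject out of the analysis.

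Finally, the study is exploratory and tests no hypothesis, and SAP 13.2 also lists V4 tables for the FAS, which is analysed by randomised arm. That limits the damage, but the FAS tables are not the topline ones.

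**Conclusion.** The point holds for the Week 1 grouping and the V4 analysis: it should be fixed, but it does not undermine the study. On the plain reading of SAP 5.5.1, smoking before randomisation enters the variable that sets the Week 1 arm. A fully abstinent SA subject with two cigarettes on V3 scores 6.7 to 12.0/month against a limit of 5, and more cigarettes score higher. This rests on three assumptions: that the V3 entry is summed, that at least two cigarettes were smoked that day, and that 5/month applies to the AEECS. How many subjects would be affected cannot be derived from the documents. A reader might extend the point to the V43 training results, but the Overall grouping is barely touched for an abstinent subject.

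**What to change.** In SAP 5.5.1 to 5.5.3, state that product use is summed from the day after V3, that the V3 diary entry belongs to the V2-V3 baseline period, and that the denominator is counted over the same dates as the sum. Apply the same start date to the covariate for cigarette consumption from randomisation to each visit in SAP 9.6.1.1.1 and 9.6.1.1.2. At nominal timing, the day after V3 through V4 is 7 dates, which agrees with the SAP's own example.

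The cost is one sentence and a date condition in the derivation. Use in the hours after randomisation on V3 would not be counted, which is a small loss.
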